CPEP	Continuous Positive Expiratory Pressure
CPT	Chest Physiotherapy
CRF	Case Report Form
CRO	Contract Research Organization
FDA	Food and Drug Administration
GCP	Good Clinical Practice
HIPAA	Health Insurance Portability and Accountability Act
ICU	Intensive Care Unit
IPPB	Intermittent Positive Pressure Breathing
IPV	Intrapulmonary Percussive Ventilation
IRB	Institutional Review Board
IV	Intravenous
LE	Lung Expansion
LOMV	Length of Mechanical Ventilation
LOS	Length of Stay
MV	Mechanical Ventilation
NIV	Noninvasive Ventilation
NSQIP	National Surgical Quality Improvement Program
OSA	Obstructive Sleep Apnea
PPC	Postoperative Pulmonary Complication
PRF	Postoperative Respiratory Failure
RCT	Randomized Controlled Trial
SOP	Standard Operating Procedure

Hill-Rom®	Evaluation of a practice change to include The MetaNeb® System to reduce postoperative pulmonary complications	Page 6 of 31
	CBI 8 September 2016	Rev C Protocol #: CR-RR2015-001

Protocol Synopsis

Product Name:	The MetaNeb® System
Protocol Number:	CR-RR2015-001
Protocol Title:	Evaluation of a practice change to include The MetaNeb® System to reduce postoperative pulmonary complications
Objective(s):	To determine if a therapy regimen including treatment with The MetaNeb® System has a positive impact on the rate of pulmonary complications that occur in high risk post-operative patients.
Endpoints:	
Primary Endpoint:
 
Significant Postoperative Pulmonary Complication (PPC): One or more of the following that occurs within seven (7) days of the post-surgical admission will be considered a Significant Postoperative Pulmonary Complication (PPC)
 
 • Patient Requires Prolonged Mechanical Ventilation (> 24 hours from post-surgical admission). • Patient requires prolonged respiratory support for > 24 hours from post-surgical admission • Diagnosis of Pneumonia Within Seven (7) Days • Readmission to ICU for pulmonary complications within seven (7) days of post-surgical hospital admission. 
Secondary Endpoints:
 
 • Requirement for invasive mechanical ventilation for > 48 hours • Requirement for respiratory support for > 48 hours • ICU Length of Stay (LOS) • Hospital Length of Stay (LOS) • Time on Mechanical Ventilation • Readmissions to ICU • 30-day Readmissions to Hospital
Study Design:	Non-randomized facility (or hospital) level pre-post intervention study

Methods:	
The study will be conducted in two stages. In Stage I of the study, a retrospective review of medical records for post-surgical patients, who received STANDARD THERAPY as defined by current hospital and respiratory care department policies and procedures will be performed. In Stage II, a CHANGE IN PRACTICE will be made and patients will receive standard care with the addition of therapy with The MetaNeb® System. Demographic, clinical & outcome data will be collected for eligible patients during the two stages of the study. Study staff will collect data from the medical records, following a protocol determined schedule.

Treatment of Subjects:	
The treatment protocol used for Respiratory Care during the STANDARD THERAPY period of the Study is that which was prescribed by the patient's health care team in the routine standard care of each patient. Respiratory Care therapies include those therapies that were ordered and/or were delivered for the care of patients as determined by standard hospital and/or Respiratory Care department policies and procedures. The STANDARD THERAPY period is one year prior to initiation of the study. Data will be collected retrospectively.
 
The treatment protocol used for Respiratory Care (excluding airway clearance and lung expansion interventions) during the CHANGE IN PRACTICE period of the Study will include care and therapy prescribed by the patient's health care team in the routine standard care of each patient. Other components of the patients respiratory care regimen will remain the same as during the standard therapy period, however the CHANGE IN PRACTICE will incorporate the use/treatment with The MetaNeb® System. Use of The MetaNeb® System will follow the labeling of the device. During Stage II, therapy with The MetaNeb® System will be delivered per treatment procedures. Other standard airway clearance and lung expansion therapies typically delivered by Respiratory Therapy will not be delivered during Stage II.

Duration of Participation:	
The Study will take approximately fifteen months to complete, from the time of study initiation through completion of data analysis.
 
The duration of study participation for prospectively enrolled subjects will be the duration of each patient's hospital stay with follow-up thirty days after discharge from the hospital.

Number of Subjects:	The sample size will be approximately 400 patients, 200 in the retrospective STANDARD THERAPY group and 200 in the prospective CHANGE IN PRACTICE group.		
Study Population:	The study population consists of adult post-surgical patients who have undergone thoracic, aortic or upper abdominal surgery who are at high risk for PPCs.		
Inclusion/Exclusion Criteria:	
Inclusion Criteria:
 
Patients who meet all of the following criteria will be included in the study:
 
• Age \geq 18 years• Post-thoracic, -upper abdominal or -aortic surgery• Open surgical procedure• Incision at or above the umbilicus• High risk defined by:
• Documented ASA class \geq 3 
OR
 
• Documented ASA class 2 AND One or more of the following:
• Current smoker or smoking history within past 6 months• History of COPD• Documented obesity and/or BMI \geq 30 kg/m²• Age \geq 75 
Exclusion Criteria:
 
Patients who meet any of the following criteria will be excluded (or will be exited) from the study:
 
• Contraindication to Continuous High Frequency Oscillation (CHFO) therapy (e.g. untreated tension pneumothorax)• Minimally invasive, or “... scopic” procedure.• Spinal surgery involving a posterior approach• Surgery for organ transplant• Chronic invasive positive pressure ventilation (PPV)		

Statistical Methods:	
Descriptive summary statistics will be provided for demographics, the primary and secondary endpoints. Continuous data will be summarized with N, mean, median, standard deviation, min, and max. Categorical data will be summarized with the number and percent of patients in each category. Time to event data (ex. Time to readmission) will be summarized with methods appropriate for survival data including a Kaplan-Meier plot.
 
Ninety-five percent (95%) confidence interval will be computed for the primary endpoint, the incidence of significant postoperative pulmonary complications. Incidence rates for various demographic subsets, surgery types, and different population subsets may be presented as outlined in the statistical analysis plan document, to be published prior to study completion. Stage I and Stage II incident rates will be compared for the purpose of identifying any statistical associations that can be attributed to use of The MetaNeb® System.
		
----------------------	---	--	--

Hill-Rom®	Evaluation of a practice change to include The MetaNeb® System to reduce postoperative pulmonary complications	Page 10 of 31
CBI	8 September 2016	Rev C Protocol #: CR-RR2015-001

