3.0 Study Design

3.1 Overview of Study Design

3.1.1 Design:

This is a non-randomized facility level pre-post intervention study conducted in two stages for the primary purpose of evaluating the effect of The MetaNeb® System on postoperative pulmonary complications in high risk patients undergoing thoracic and

Hill-Rom®	Evaluation of a practice change to include The MetaNeb® System to reduce postoperative pulmonary complications	Page 13 of 31
CBI	8 September 2016	Rev C Protocol #: CR-RR2015-001

abdominal surgeries. The study will be conducted in two to four (2-4) tertiary academic medical facilities in the US that have not previously used The MetaNeb® System in post-thoracic, post-aortic, or post-upper abdominal surgery patients. After assessing outcomes during a baseline period, therapy with The MetaNeb® System will be introduced and incorporated into the respiratory care treatment regimens and outcomes will be assessed after the change in practice.

3.1.2 Procedure:

In Stage I of the study, a retrospective review of medical records for post-surgical patients, who received STANDARD THERAPY as defined by current hospital and Respiratory Care department policies and procedures. This will be a retrospective data collection only.

The purpose of study Stage I is to estimate the incidence of postoperative pulmonary complications in post-surgical patients receiving standard of care per hospital and Respiratory Care department procedures and policies. Data collected in Stage I will include data from the medical records of 200 randomly selected, eligible patients treated during the year prior to the CHANGE IN PRACTICE. This allows for inclusion of patients from the seasonally consistent time period as well as those from most recent time period, during which care practices are most similar.

In Stage II, a CHANGE IN PRACTICE will be made and patients will receive standard care with the addition of therapy with The MetaNeb® System. Other standard airway clearance and lung expansion therapies typically delivered by Respiratory Therapy will not be delivered during Stage II. During Stage II, data from approximately 200 patients will be collected from the medical records across the 3 sites.

Demographic, clinical & outcome data will be collected for eligible patients during the two stages of the study. Study staff will collect data from the medical records, following a protocol determined schedule.

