5.0 Study Procedures

5.1 Informed Consent:

A waiver of informed consent will be requested for patients enrolled in the study in Stage I (retrospective review of data). Informed consent must be obtained from all subjects in Stage II prior to participation as per Federal Regulations and/or the qualifying Institutional Review Board (IRB). A blank copy of the IRB-approved form must be kept on-site and by the sponsor. The signed original for each subject must be kept in the study files.

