7.2 Institutional Review

Prior to study initiation, the appropriate IRB must approve the observational study. It is the responsibility of the Investigators, in collaboration with the Sponsor, to provide the IRB with all necessary information to satisfy the individual Institution's requirements.

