## 1 Introduction

The study will be conducted in two stages.

Stage I of the study, STANDARD THERAPY, is a retrospective review of medical records for 200 randomly selected post-surgical patients, who received standard of care therapy as defined by current hospital and respiratory care department policies and procedures. Data collected in Stage I will include data from the medical records of eligible patients treated during the year prior to the start of Stage II. This allows for inclusion of patients from the seasonally consistent time period as well as those from most recent time period, during which care practices are most similar between the 2 stages.

Stage II of the study, a CHANGE IN PRACTICE will be made and patients will receive standard care with the addition of therapy with The MetaNeb® System. Other standard airway clearance and lung expansion therapies typically delivered by Respiratory Therapy will not be delivered during Stage II. Data from approximately 200 patients will be collected from the medical records at 3 sites. However, an adjustment in sample size may be made based on the incidence rate for post-operative pulmonary complications in Stage I, to allow for a robust estimate and assessment of the effect of therapy with The MetaNeb® System.

Stage II will start after gathering and analysis of data from Stage I

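### The Stage I sampling window is defined in two ways, and with about 15 months in total Stage II probably covers only part of a year, so seasonal comparability is not assured

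*Protocol*

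**What the plan says.** The Protocol synopsis (Treatment of Subjects) sets the Stage I window with "The STANDARD THERAPY period is one year prior to initiation of the study". Protocol 3.1.2 uses another anchor, taking records of "eligible patients treated during the year prior to the CHANGE IN PRACTICE". SAP 1 has "eligible patients treated during the year prior to the start of Stage II", and SAP 3 (Stage I) uses the same anchor as Protocol 3.1.2.

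Protocol 3.1.2 and SAP 1 give two reasons for taking a year. The first is season: "This allows for inclusion of patients from the seasonally consistent time period". The second is recency, since the latest patients were treated when care was most alike in the two stages.

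On the order of the stages, SAP 1 says "Stage II will start after gathering and analysis of data from Stage I". On length, the synopsis (Duration of Participation) says "The Study will take approximately fifteen months to complete, from the time of study initiation through completion of data analysis". Protocol 3.3 places the readmission review 30 days after the last patient's discharge.

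Neither document gives a Stage II enrolment period. The 200 Stage I charts are chosen at random, and no stratification by site or calendar month is described. SAP 6.3 presents the primary endpoint as proportions with 95% confidence intervals, with no adjustment for site or season.

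**The concern.** Stage I is the only comparator, and its window is the sampling frame. A site that follows the synopsis and a site that follows Protocol 3.1.2 would draw charts from different periods.

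The design has no concurrent control. Any difference in calendar coverage between the stages is therefore confounded with the device, and enrolling more patients would not remove it. Protocol 3.5.2 intends to compare the stages to find associations attributable to the device. The one-year window is the plan's stated protection on season and recency, so it matters whether the window can do that work.

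**Working it through.** There is no stated calculation to reproduce. SAP 5 reports no formal sample size determination, and the 15 months is not broken into parts. It can only be tested for consistency.

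**1. Are the two anchors the same date?**
- Protocol 7.2: "Prior to study initiation, the appropriate IRB must approve the observational study".
- Protocol 5.1: "A waiver of informed consent will be requested for patients enrolled in the study in Stage I". Stage I patients thus count as enrolled in the study.
- SAP 1 puts Stage I gathering and analysis before Stage II.

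Read together, study initiation comes before the Stage I work and Stage II comes after it. The windows are offset by the length of that work. The documents give no length, so assume 1 to 4 months. With charts spread evenly over the year, 200 × 1/12 = 17 to 200 × 4/12 = 67 of the 200 would come from months outside the other window.

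**2. Does either window fit the stated reasons?**
- Year before initiation: it omits the months of Stage I work, which are the most recent before Stage II.
- Year before Stage II: a patient operated on just before Stage II has no 7-day outcome, discharge or 30-day readmission status yet. If Stage I is gathered and analysed first, roughly the last month cannot be complete for readmission.

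**3. How long can Stage II enrol?** Take the clock to start at initiation, before the Stage I work. Follow-up is 30/30.44 = 0.99 month.

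W = 15 − Stage I work − last hospital stay − 0.99 − final analysis

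For W = 12, what remains is 15 − 12 − 0.99 = 2.01 months for Stage I work, any sample size adjustment, the last stay and the final analysis together.

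Assumed ranges (not in the documents): Stage I work 1 to 4 months, last stay 0.25 to 0.5 month, final analysis 1 to 3 months.
- Longest: 15 − 1 − 0.25 − 0.99 − 1 = 11.8 months.
- Shortest: 15 − 4 − 0.5 − 0.99 − 3 = 6.5 months.
- With no time at all for Stage I work and 1 month for final analysis: 12.5 to 12.8 months.

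In this grid, W reaches 12 only in that last case.

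**4. How large could a seasonal bias be?** Use a 10% complication rate, the midpoint of the 5% to 15% in Protocol 3.5.1. The documents give no seasonality, so two assumed patterns follow, both with no device effect.

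*Smooth seasonal swing* of relative size r around 10%, with Stage II at the worst phase. Bias in points = 10 × r × sin(πW/12)/(πW/12).

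| W (months) | r = 10% | r = 20% | r = 30% |
|---|---|---|---|
| 6 | 0.6 | 1.3 | 1.9 |
| 8 | 0.4 | 0.8 | 1.2 |
| 10 | 0.2 | 0.4 | 0.6 |
| 12 | 0 | 0 | 0 |

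*High half-year and low half-year* with rate ratio k. The low-half rate is 2 × 10%/(1 + k).
- k = 1.3 gives 8.7% and k = 1.5 gives 8.0%. A Stage II of 6 wholly low-season months would be 1.3 to 2.0 points too low.
- Nine months, six of them low-season: (2/3) × 8.70 + (1/3) × 11.30 = 9.6%, and (2/3) × 8.00 + (1/3) × 12.00 = 9.3%. The shift is 0.4 to 0.7 points.
- A Stage II weighted to the high season shifts by the same amounts the other way, against the device.

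For scale, the standard error of the difference is √(2 × 0.10 × 0.90/200) = 3.0 points.

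**The case against.** The strongest reply is that the body of the protocol and the SAP agree with each other, so only a synopsis line is out of step. The word initiation is also undefined. If it meant the start of Stage II, the two windows would coincide, and 12 + 1 + 2 = 15 months would just fit. The 15 months is approximate, and every duration used for Stage I work and final analysis is assumed. This stands as a limit on the timeline argument. It does not remove the conflict: Protocol 5.1 and 7.2 with SAP 1 favour different dates, and the synopsis does not say otherwise.

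A reader might infer that the plan promises seasonal matching and fails to deliver it. The documents do not support that. They say only that a year allows seasonally consistent patients to be included, and a 12-month window contains every calendar month once. What is missing is any step that makes the stages comparable by month.

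A reader might also infer a spurious relative reduction of 13% to 20%, which is 1.3 to 2.0 points on 10%. That needs an assumed seasonal ratio and a Stage II of six wholly low-season months, shorter than the 6.5-month minimum found above. It also shows only the direction that favours the device.

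Finally, confounding by time is inherent in an openly declared pre-post design, and calendar adjustment does not remove a secular trend. That is correct, and it limits what the fix can achieve.

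**Conclusion.** The conflict in the window is wrong as written. The two rules select different charts. The synopsis rule leaves out the most recent months that the plan says it wants, and the rule in Protocol 3.1.2 and the SAP cannot be complete up to Stage II under the SAP's own sequence.

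That Stage II probably covers only part of a year is an inference. It rests on the clock starting before the Stage I work and on that work taking at least about a month. On that reading, seasonal comparability is not assured, which is weaker than saying that it fails. The bias is probably modest: at most about 2 points at a 10% rate under the assumed patterns, less than one standard error of 3.0 points, and in either direction. It would nevertheless be systematic. Stratified sampling and an adjusted comparison are a cheap improvement and should be made.

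**What to change.** 1. Use one Stage I window in the synopsis, Protocol 3.1.2 and SAP 1 and 3. Give it a cut-off that leaves time for 30-day readmission, abstraction and analysis before Stage II starts.
2. State the planned Stage II enrolment period, and when the 15-month clock starts.
3. Draw the 200 Stage I charts at random within strata of site and calendar month across the year. This is almost free in a chart review.
4. In the SAP, add a Stage II versus Stage I comparison adjusted for site and season alongside the crude rates. A model with site and season main effects, or standardisation with coarse season strata, would serve. Avoid full site-by-quarter cells: with 3 sites, 200/12 is about 17 charts per cell, or 1.7 events at 10%.

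The cost is wording, slightly wider intervals and a little more analysis.

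Restricting Stage I to the calendar months that Stage II covers should not be the main approach. With a 9-month Stage II, for example, it would drop the three most recent months of a year ending at the change in practice. If only the matching charts of the 200 were kept, about 150 would remain and the standard error would rise from 3.0 to √(0.09/150 + 0.09/200) = 3.2 points.

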1.0 Introduction

1.1 Background and Significance

Post-operative pulmonary complications (PPC) are associated with significant excess morbidity, mortality and healthcare expenditure. The incidence of “important” PPCs, across all surgeries, is approximately 2-5% in the general surgical population. There are factors, however, that place certain patients, and patients with certain procedures, at considerably higher risk for PPCs. One of the key factors in development of PPCs is the type of surgery. Following upper abdominal and thoracic surgery, pulmonary complications are the most common surgical complications. Other risk factors include advanced age, American Society of Anesthesiologists (ASA) physical status classification score ≥ 2 , functional dependency, congestive heart failure and chronic obstructive pulmonary disease. Of these, ASA score ≥ 2 and functional dependency have consistently been associated with a higher rate of significant PPCs such as post-operative respiratory failure (PRF). PRF requiring prolonged mechanical ventilation (MV) or re-intubation accounts for the majority of poor outcomes and high economic costs.^[1-4] Other risk factors that have been associated with increased risk of PPCs include history of COPD, smoking history and BMI $\geq 30 \text{ kg/m}^2$.^[1-5]

Although PPCs are an incompletely understood multifactorial syndrome, atelectasis is recognized as a critical component.^[6] Evidence has shown that atelectasis is a common precursor and concomitant feature of PPCs. Nearly all patients undergoing major surgery experience some degree of transitory, clinically unimportant atelectasis, most of these patients do not require aggressive therapy. There is, however, a more urgent need to treat atelectasis in subpopulations of high-risk individuals, in order to prevent more serious complications including progression to PRF.^[7]

A variety of strategies have been shown to reduce the risk for development of post-operative atelectasis to at least some degree. These include but are not limited to pain control, monitoring of respiratory-depressing medications, selective use of nasogastric decompression, secretion mobilization techniques and lung expansion (LE) therapies.^[6-9] However, the generally poor quality of clinical trials to evaluate these methods provides only limited, inconclusive evidence of efficacy. Among published studies, LE using continuous positive airway pressure (CPAP) breathing, particularly when used in hypoxicemic high-risk patients, is the only modality to date demonstrating comparatively strong evidence.^[10,11] In a systematic review of qualifying randomized controlled trials (RCT), Lawrence et al sought to evaluate interventions intended to reduce the incidence of atelectasis, pneumonia and PRF following non-cardiothoracic surgery.^[11] Their meta-analysis pooling all eligible studies to determine “strength of evidence” found that only LE therapy merited a grade of “A”. These

Hill-Rom®	Evaluation of a practice change to include The MetaNeb® System to reduce postoperative pulmonary complications			Page 11 of 31
	CBI	8 September 2016	Rev C	Protocol #: CR-RR2015- 001

LE therapy techniques included incentive spirometry (IS), deep breathing techniques, chest physiotherapy (CPT), intermittent positive pressure breathing (IPPB) and continuous positive pressure (CPAP). Although data did not permit identification of a “best” modality, they did allow the conclusion that all lung expansion therapies reduced PPC by > 50% compared with no treatment. Well-designed studies are needed to distinguish which LE approach has the greatest potential to optimize patient care, clinical outcomes and cost savings.

